The web-based Survivorship Care Plan in Reproductive Health (SCP-R) intervention was developed to address unmet informational and clinical management needs for hot flashes, fertility-related concerns, contraception, and sexual health in YBCS. Research findings, professional society guidelines and clinical expertise on these reproductive health issues were curated into screening and management strategies that will be delivered to YBCS and their HCPs via the SCP-R intervention. A web-based intervention and text message support were chosen to enhance intervention accessibility.

This report details the design, recruitment, and baseline characteristics of YBCS and HCP participants of the randomized controlled trial testing the efficacy of the SCP-R intervention on improving reproductive health in YBCS. We hypothesize that YBCS who receive the SCP-R intervention will be more likely to improve on at least one of four targeted reproductive health outcomes (hot flashes, fertility-related concerns, sexual health, and contraception) compared to waitlist controls.

Material and Methods

The SCP-R trial will test the efficacy of a 24-week, web-based educational intervention with text message support in improving reproductive health issues experienced by female YBCS.

Following online eligibility screening and consent, YBCS complete an enrollment questionnaire and undergo a 7-day run-in period for reporting daily hot flash frequency and severity via text messaging. Adherent participants are randomized in a 1:1 ratio to the intervention or waitlist control arm. Participants in the intervention arm receive access to the full web-based SCP-R intervention and reproductive health text message prompts, while participants in the waitlist control arm receive access to a list of curated web-based resources and study adherence text messages. All participants will be followed for 24 weeks, report daily hot flash frequency and severity via text messaging, and complete a 12-week and a final 24-week questionnaire.

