YBCS are eligible if they report experiencing at least one of the four targeted reproductive health issues: hot flashes (\geq 4 per day with \geq 1 at least moderate in severity), moderate to high pregnancy and/or fertility concerns (fertility or pregnancy subscale score >3 on the Reproductive Concerns After Cancer Scale), not using contraception or using a less effective method (barrier or fertility awareness methods, withdrawal, or spermicides), or vaginal atrophy symptoms (\geq 1 symptom of vaginal dryness, irritation, soreness or dyspareunia over the past 4 weeks reported as at least moderate in severity). Additional eligibility criteria include: ages 18-50 at study enrollment, diagnosed with stage 0-III breast cancer between ages 18-45, completed primary cancer treatment including surgery, chemotherapy and radiation, are not pregnant at enrollment, are able to read English and access the Internet, and are able to complete daily text message hot flash diaries.

YBCS are recruited from the following sources: (1) cancer advocacy organizations including the Young Survival Coalition, Susan G. Komen San Diego and Army of Women-a program by the [name] Research Foundation, (2) referrals from health care providers and patient advocates, (3) Research Match, (4) previous observational studies conducted by the investigators. Interested YBCS are directed to the study web portal to create a secure personal account, followed by online access to study description, screening for eligibility and consent.

Consented participants complete the enrollment questionnaire and undergo a 7-day daily hot flash text message run-in period. Participants receive two daily text messages prompting them to report the number of hot flashes and severity of each hot flash (mild, moderate, severe, or very severe) in the previous 24 hours. Participants with at least 70% adherence over 7 days are then randomized.

YBCS randomization

Computerized, blocked randomization with equal allocation to intervention and waitlist control arms was undertaken. Randomization is stratified by the four a priori reproductive health issues in order to

maintain balance between the intervention and waitlist control groups with regard to these factors. Fifteen unique strata were created based on possible combinations of experiencing one or more of the four late effects.

HCP eligibility, recruitment, consent, enrollment and procedures

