We will deploy several approaches to motivate YBCS participants to complete the study. Participants will receive up to \$100 in Amazon gift cards for completing each of 3 questionnaires and daily hot flash text messages. Weekly, automated reminder emails to complete study tasks will be sent via the web platform. Telephone call and/or text message reminders will be undertaken for overdue tasks for up to 5 contacts. On hot flash text messages, daily reports will be generated to monitor responses and identify those who had not responded in \geq 3 consecutive days for study staff contact.

HCP participant adherence and retention

HCP participants will receive up to \$40 in Amazon gift cards for completing each of 2 questionnaires. Weekly, automated email reminders to complete study tasks and view their patient's SCP will be sent via the website platform. HCPs who opted to participate via paper materials will be contacted by telephone calls to their medical practice to confirm receipt and encourage completion overdue tasks for up to 5 contacts. If a final questionnaire is not received within two months of mailing, questionnaires will be resent.

Statistical Analysis

The primary analysis will be intent-to-treat. The primary composite outcome will be an improvement in at least one reproductive health issue over the 24 week study, defined as: $\geq 50\%$ improvement in enrollment hot flash score, $\geq 50\%$ improvement in enrollment vaginal atrophy symptom score, use of highly effective contraceptive methods (sterilization, long-acting reversible contraception, injectables, pills, patch or vaginal ring), and fertility and pregnancy concern subscale scores <3. Logistic regression models will be used to test for differences by intervention versus control arm; odds ratios with 95% confidence intervals for intervention effect will be reported.

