To quantify intervention effects on each of the four reproductive health issues, we will also undertake secondary analyses to compare changes in each issue separately. As participant responses will be measured at enrollment, 12 and 24 weeks, we will compare each health issue outcome between the intervention and waitlist control groups using linear mixed effect models for the continuous outcomes (hot flash score, vaginal atrophy symptom score, fertility concerns score) and GEE models for binary outcomes (use of effective contraceptive method). Best linear unbiased predictors from the mixed models will also be used to impute missing outcomes for the primary composite outcome. Similar analysis will be conducted for secondary outcomes, which include additional YBCS-reported symptoms and actions, as well as healthcare provider preparedness and confidence.

Sample size

YBCS participants will be randomized into two arms: intervention and waitlist control. We will measure outcomes at enrollment, 12 weeks, and 24 weeks. Leveraging published data on hot flashes [31], we based sample-size calculations on detecting meaningful changes in hot flash frequency and score. With a sample size of 50/arm, there will be 80% power to detect a 0.57 effect-size between groups on hot flash score changes from baseline to 24 weeks based on a 2-sided t-test with alpha =0.05. This effect-size translates to a group difference of 1.2 hot flashes or 3 units in the hot flash score, if we assume the standard deviation of the change was 2 hot flashes or 5 score units per patient per day. Incorporating all the repeated measurements on each participant should ensure sufficient power to detect an even smaller effect size. In particular, assuming 2 post-randomization measures with autocorrelation 0.5, there is 80% power to detect a 0.44 effect size with 50 samples in each arm and 2-sided significance level 0.05.

Considering the composite primary outcome of improvement in at least 1 reproductive health issue, we have 80% power to detect a 27% group difference, e.g., 25% in the control arm and 52% in the treatment improve on at least one outcome. Given that some participants may have the same healthcare provider, we account for a clustering effect as follows: we assume as a worst-case scenario that on average 3 participants shared a provider, and that intraclass correlations (ICC) of the study outcomes due to a shared physician is 0.1. This results in a design

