effect of 1.2, requiring us to inflate the sample-size by 20%. We further anticipate 20% sample size loss due to the run-in period prior to randomization, and an additional 20% drop-out rate. Hence, we aim to enroll 196 participants and randomize 157 to ensure sufficient power.

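### The primary logistic model is not adjusted for the four issues that stratify randomization, so the planned test is mildly conservative and gives up some power

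*Combined protocol and SAP*

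**What the plan says.** On design, the YBCS randomization section states "Computerized, blocked randomization with equal allocation to intervention and waitlist control arms was undertaken". It continues "Randomization is stratified by the four a priori reproductive health issues in order to" keep the arms comparable on them, and adds "Fifteen unique strata were created based on possible combinations of experiencing one or more of the four late effects" (2^4 − 1 = 15).

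On analysis, the Statistical Analysis section defines the endpoint: "The primary composite outcome will be an improvement in at least one reproductive health issue over the 24 week study". For the test it says "Logistic regression models will be used to test for differences by intervention versus control arm", reported as odds ratios with 95% confidence intervals. No covariate is named there, and none is named for the secondary mixed and GEE models. Nowhere do the stratification factors enter an analysis.

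On size, the Sample size section bases the composite on 80% power for, as an example, "25% in the control arm and 52% in the treatment improve on at least one outcome", and concludes "we aim to enroll 196 participants and randomize 157 to ensure sufficient power".

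**The concern.** Blocking within strata forces the arms to be nearly balanced on the four issues. The true sampling variance of the arm difference then excludes most between-stratum variation, but the standard error from an arm-only model still includes it. If the issues predict the outcome, that standard error is too large: the test rejects less often than 5% under the null and loses power under the alternative.

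The endpoint makes prognostic strata plausible, although the documents give no estimate. Two components are changes from an enrollment score, so a woman with more qualifying issues has more ways to succeed. The contraception and fertility components are statuses during follow-up, which a woman without that issue may already meet at entry. On either reading, baseline issue status bears on the outcome.

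What is at stake is efficiency, plus clarity about the effect measure. Odds ratios with and without prognostic covariates estimate different quantities, and covariate choice left unstated could be made after outcomes are known.

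**Working it through.** **1. The plan's own figure.** Inputs from the Sample size section: 50 per arm, 25% and 52%. Two-sided alpha 0.05 is stated there for hot flashes and assumed here for the composite. With pooled variance under the null, power = Φ{[0.27√50 − 1.96√(2 × 0.385 × 0.615)] / √(0.25 × 0.75 + 0.52 × 0.48)} = Φ{(1.909 − 1.349)/0.661} = Φ(0.848) = 80.2%. The stated 80% reproduces, as an unadjusted calculation.

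**2. Why arm-only is conservative.** If the strata explain a fraction R² of the outcome variance and balance is perfect, the arm-only Wald test has size of about 2{1 − Φ(1.96/√(1 − R²))}. R² = 0.036 gives 4.6%, 0.13 gives 3.6% and 0.279 gives 2.1%.

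**3. Main simulation.** 15,000 replicates per cell, with two sample sizes: 157 × 0.8 = 125.6, run as 126; and 125.6/1.2 = 104.7, run as 104, after the plan's clustering design effect of 1.2. Assumptions not in the documents:
- blocks of 4 and issue prevalences of 45/45/40/60%;
- only issues present at enrollment can improve;
- stratum response = 1 − exp(−h × sum of weights), with h solved so that the marginal rates are exactly 25% and 52%;
- a flat rate, or weights 1:1:1:1, 1:1:1:6 or 1:1:1:20. Control-arm stratum rates are then 0.25, 0.13–0.44, 0.06–0.40 and 0.02–0.39.

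Adjusted means arm plus four issue indicators, with Cochran-Mantel-Haenszel (CMH) used where that model failed.

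| n | Issues | Size, arm-only | Size, adjusted | Power, arm-only | Power, adjusted | Gain (points) |
|---|---|---|---|---|---|---|
| 126 | not prognostic | 4.4% | 4.8% | 88.8% | 89.2% | 0.4 |
| 126 | similar | 4.3% | 5.0% | 89.4% | 90.8% | 1.4 |
| 126 | one 6× | 4.0% | 5.2% | 90.1% | 93.0% | 2.9 |
| 126 | one 20× | 3.4% | 5.1% | 91.1% | 95.7% | 4.6 |
| 104 | not prognostic | 4.6% | 5.1% | 81.7% | 82.4% | 0.7 |
| 104 | similar | 4.4% | 5.1% | 82.1% | 84.5% | 2.4 |
| 104 | one 6× | 4.2% | 5.5% | 84.0% | 88.1% | 4.1 |
| 104 | one 20× | 3.4% | 5.4% | 84.1% | 91.6% | 7.5 |

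Part of the shortfall below 5% is ordinary Wald behaviour. An exact arm-only Wald calculation without stratification gives size 4.6% and power 82.7% at 52 per arm, and 4.8% and 89.0% at 63 per arm.

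**4. Different response model.** Additive log-odds effects, prevalences 40/50/40/60%, 4,000 replicates, N = 100, Wald tests:

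| Log-odds per issue | Size, arm-only → adjusted | Power, arm-only → adjusted | Conditional log odds ratio |
|---|---|---|---|
| 0 | 5.0% → 5.4% | 79.9% → 80.8% | 1.179 |
| 0.5 each | 4.2% → 5.2% | 80.4% → 82.4% | 1.230 |
| 1.0 each | 3.6% → 5.4% | 82.6% → 86.6% | 1.375 |
| 1.5, −0.5, 1.5, 0.5 | 3.6% → 5.8% | 82.5% → 88.0% | 1.461 |
| 2, −1, 2, 1 | 2.1% → 5.0% | 83.2% → 91.7% | 1.683 |

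The arm-only sizes follow the formula in step 2: R² is 0.036 for 0.5 each, 0.13 for 1.0 each and 0.279 for the last row. Adjusted likelihood-ratio tests ran at 5.8–6.5%. The last column shows the change of effect measure. The marginal odds ratio is (0.52/0.48)/(0.25/0.75) = 3.25, while the conditional one runs from 3.25 to e^1.683 = 5.4 for the same marginal rates.

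**5. Feasibility.** 126/15 = 8.4 women per stratum on average, too few for 14 stratum dummies. In the main simulation under the null, the four-indicator model failed through separation in under 0.1% of replicates with similar issues, 2–4% with one 6× issue and 23–29% with one 20× issue. CMH never failed. Its size was 4.6–5.2%, and its power was 88.2/90.0/92.4/95.4% at 126 and 81.0/83.4/87.2/90.9% at 104 (same row order as the first table).

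**The case against.** The strongest reply is that nothing is broken. The arm-only test is valid, and its lowest power in the main simulation, 81.7%, still clears the stated 80%. That is correct and limits how serious the point can be.

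The larger gains also rest on pessimistic or unsupported inputs:
- The 104 figure uses a worst-case clustering assumption, whereas the Blinding section reports only 3 HCPs nominated by more than one participant.
- The analysis is by intent to treat with imputation, so up to 157 women may be analysed. At that upper bound the gains shrink to 0.3, 1.0, 1.4 and 2.2 points, with arm-only power already 94–96%. Imputation does not restore full information, so the truth lies below that bound.
- No text supports a 20× weight, or any other weight.

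These points stand, and make 126 without the 20× case the fair headline.

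Part of the gain comes from comparing tests of unequal size. With the adjusted test calibrated to exactly 5% at 104, the gain is about −0.6 (not prognostic), 2.1 (similar) and 3.5 points (6×). So the 0.7-point gain with non-prognostic issues is not real efficiency, but most of the gain with prognostic issues is.

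Finally, the plan read literally yields a marginal odds ratio, and it is the remedy that makes it conditional. That is fair. It is a reason to state the measure explicitly, not a reason to ignore the strata.

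**Conclusion.** The point holds as a modest efficiency and specification gap. The plan stratifies on four issues and uses none of them in the primary test. Followed as written, that test is somewhat conservative (size 3.4–4.4% at 126 evaluable women in the main simulation) and forgoes power: typically 1 to 3 points at 126, nothing material if the issues are not prognostic, and up to 4.6 points if one issue dominates. The 104 results, with gains up to 7.5 points, are a pessimistic bound. Neither validity nor the stated 80% power is threatened.

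The direction is secure, because two different response models agree. The size is not: it rests on assumed prevalences, block size and prognostic strength, and on a rule that only issues present at enrollment can improve. The mixed and GEE models were not examined, and no claim is made about them.

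**What to change.** Add to the Statistical Analysis section that the primary logistic model includes arm and the four baseline issue indicators as main effects, not stratum dummies, and that the arm effect is judged by a two-sided Wald test. State that, if separation prevents the fit, a CMH test over the 15 strata replaces it. CMH is a better fallback than a Firth-penalized Wald test, which had lower power in every cell (size 3.9–4.3%). Report the odds ratio as conditional on the issues, with a standardized risk difference beside it.

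Prespecifying CMH as the sole primary test is a reasonable alternative. It avoids a data-dependent choice of test and comes within 1.4 points of the adjusted model's power in every cell of the main simulation.

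The cost is one or two sentences and no additional participants, since the indicators are already held for randomization. The downsides are a conditional odds ratio, an adjusted Wald size that can sit slightly above 5% (up to 5.5% in the main simulation and 5.8% in the second), and the need for the fallback.

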Contraception outcomes will be analyzed in participants at risk of unintended pregnancy, defined as having a uterus and at least one ovary, sexually active in the 24 months prior to or during the study, ≤ 45 years old. For the primary analysis, use of highly effective birth control methods (intrauterine devices, female sterilization, male partner sterilization, combined hormonal contraception, progestin implants or injections) during follow up will be considered an improvement for the primary composite outcome. Secondary contraceptive outcomes will include confidence to talk with a HCP about contraception, plans to implement and implementation of suggestions from the contraception SCP.

Sexual health will be measured the Vaginal Atrophy Symptoms Score, a 4-item scale on vaginal dryness, soreness, irritation and dyspareunia experienced in the prior 4 weeks [29]. Each item has a 4-point Likert scale response (0-none, 1-mild, 2-moderate, 3-severe). The scale will be summarized by averaging responses, with higher scores indicating a greater level of vaginal atrophy. For the primary analysis, a decrease of 50% in the score will be defined as an improvement in vaginal symptoms for the primary composite outcome. Secondary outcomes included sexual desire, arousal, orgasm and pain via the 19-item Female Sexual Function Inventory (FSFI), confidence to talk with a HCP about vaginal symptoms and sexual health management, plans to implement and implementation of a suggested tip from the intervention materials.

HCP measures

HCP preparedness and confidence in talking to their patients about each of the four reproductive health issues will be measured. Each preparedness item had a 4-point Likert scale response (very unprepared, unprepared, prepared, and very prepared). Each confidence item had a 7-point Likert scale response (not at all confident, slightly confident, somewhat confident, moderately confident, quite confident, very confident, and extremely confident). Demographic, medical specialty, and experience and volume of breast cancer patients, and satisfaction with SCP materials will also be measured.

YBCS participant adherence and retention

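### Missing primary outcomes are filled with BLUPs and then cut at thresholds, which misclassifies dropouts, and the rule cannot fill the contraception component at all

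*Combined protocol and SAP*

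**What the plan says.** The primary outcome is "an improvement in at least one reproductive health issue over the 24 week study" (Statistical Analysis). It counts a fall of at least 50% in the hot flash score, a fall of at least 50% in the vaginal symptom score, fertility and pregnancy subscale scores below a cut-off, or use of a highly effective contraceptive. It is tested by logistic regression under intent-to-treat, and "odds ratios with 95% confidence intervals for intervention effect will be reported".

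The component models appear in the same section: linear mixed models for the three scores, and "GEE models for binary outcomes (use of effective contraceptive method". Data come from three occasions: "participant responses will be measured at enrollment, 12 and 24 weeks". On missing data there is one sentence: "Best linear unbiased predictors from the mixed models will also be used to impute missing outcomes for the primary composite outcome". The plan describes no multiple imputation, no allowance for imputation in the standard error, no rule for missing contraceptive use and no sensitivity analysis for missing data.

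The Sample size section assumes "25% in the control arm and 52% in the treatment improve on at least one outcome" and "an additional 20% drop-out rate", with 157 randomized.

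**The concern.** On the direct reading, the BLUP stands in for the missing score and is then compared with the cut-off. A conditional mean says where a participant is expected to be, not how likely she is to cross a threshold. If the expected value falls short, nearly all similar dropouts become non-responders; if it just clears the threshold, nearly all become responders. Logistic regression then treats these values as data.

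For contraception the rule does not work at all. GEE is a marginal model without random effects, so there is no participant-level BLUP, and the analyst would have to invent a rule, possibly after seeing data.

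At stake are the responder rates and odds ratio of the primary analysis. Twenty per cent of 157 is about 31 participants.

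**Working it through.** **1. The plan's own figure.** For 25% vs 52%, two-sided alpha 0.05 and 80% power, n per arm = [1.96·√(2·0.385·0.615) + 0.842·√(0.25·0.75 + 0.52·0.48)]² / 0.27² = (1.349 + 0.556)² / 0.0729 ≈ 50. Power at 50 per arm is 80.2%, so the stated 80% is reproduced. The true odds ratio is (0.52/0.48)/(0.25/0.75) = 3.25.

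**2. The mechanism, for one score.** The plan gives an SD of change of 5 and a correlation of 0.5. Its correlation is between two post-randomization measures; extending it to enrollment is an assumption. Then 2σ²(1 − 0.5) = 25, so σ = 5 per visit.

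- With enrollment data only, the week-24 prediction is m24 + 0.5·(Y0 − m0). The cut-off is 0.5·Y0. The gap is m24 − 0.5·m0, the same for every participant in an arm.
- The SD of Y24 − 0.5·Y0 is 5·√(1.25 − 0.5) = 4.33.
- At a true rate of 25% the gap is +0.674 × 4.33 = +2.92, so every such dropout is called a non-responder. At 52% it is −0.050 × 4.33 = −0.22, so every one is called a responder.
- With 12-week data as well, the proportions called responders are about 2% and 56%.

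Estimation error blurs this. Simulating 78 per arm with best-prediction filling (half of dropouts with enrollment data only, half with week 12 too) gave 20–21% vs 53–54%, OR 4.2–4.5, for correlations of 0.3 to 0.7. This is a single score, not the primary composite.

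**3. The four-issue composite.** From the plan: 25% vs 52%, 20% drop-out, 78 per arm, SD 5 and correlation 0.5. Assumed:

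- drop-out completely at random, with 60% of dropouts also missing week 12;
- issues independent, each present with probability 0.5 and at least one present;
- component rates all equal at 12.9% vs 30.8%. Check: 1 − [(1 − 0.5·0.129)⁴ − 0.5⁴]/(1 − 0.5⁴) = 25%, and 52% with 0.308;
- hot flash score mean 13, truncated at 5; vaginal score mean 1.4, SD 0.6; one fertility score, mean 4.0, SD 0.7, cut at ≤3.

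The model was a random-intercept model with arm-by-visit means, with 3,000 replicates. Odds ratios are computed from average rates.

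| Week 24 | Overall rates | OR |
|---|---|---|
| Truth | 25% vs 52% | 3.25 |
| Missing contraception = non-use | 20% vs 44% | 3.11 |
| Contraception fully observed | 21% vs 47% | 3.24 |

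The second row can be rebuilt by hand. Dropouts are called responders 0.3% vs 11% of the time, so 0.8·25 + 0.2·0.3 = 20.1% and 0.8·52 + 0.2·11 = 43.8%. The third row follows similarly from 7% vs 25%: 21.4% vs 46.6%.

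With missing contraception still counted as non-use, fewer issues per woman (probability 0.25) gave OR 3.51 and more (0.75) gave 2.92.

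**4. One score driving response.** With vaginal symptoms improving in 36% vs 70% and other components in 5% vs 10–15%, true rates of 25.5% vs 50.3% (OR 2.95) became 21.1% vs 50.7% (OR 3.85). The ratio is 3.85/2.95 = 1.31. A similar set-up moved 26% vs 49% (OR 2.8) to 21% vs 50% (OR 3.7).

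**5. Mitigation.** Counting a response at either visit gave 21% vs 45% (OR 3.01), and the share of outcomes resting on imputation falls from 20% towards 16% if daily texts also supply the hot flash score. With texts supplying that score for all dropouts, rates were 21% vs 47% (week 24) and 22% vs 47% (either visit).

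**6. Composite type I error (week 24 / either visit), equal component rates, missing contraception = non-use.**

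| Drop-out by arm | True rate | Type I error |
|---|---|---|
| Equal, 20% | 25% | 4.7% / 4.3% |
| Equal, 20% | 50% | 6.2% / 4.5% |
| 15% vs 25% | 25% | 6.4% / 5.5% |
| 10% vs 30% | 25% | 11.3% / 9.4% |

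Monte Carlo error is about ±0.8 points at 5%. With contraception observed, the 10% vs 30% week-24 figure is about 8%.

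**The case against.** The strongest reply is that the test hardly changes. With equal drop-out and equal component rates, type I error is 4.3–6.2%, and power is 89% against 90–92% under multiple imputation. The odds-ratio shift in those scenarios is at most |ln(2.92/3.25)| = 0.11, under a third of the standard error of about 0.37. Part of the distortion also comes from counting missing contraception as non-use, which the plan does not say; with contraception observed the week-24 odds ratio is almost unchanged. All of this stands, and it limits the point to a fixable defect in estimation and specification.

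Three stronger readings are tempting, and the documents support none of them.

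- *The rule lowers both arms' rates, so it is conservative, or its error lies within some 10% either way.* Both patterns come from equal component rates. Step 4 breaks them, and the plan gives no component-level response rates.
- *The rule inflates the false-positive rate.* Large inflation with equal drop-out appeared only for a single score judged at week 24 (16–27% at a true rate of 50% in the step 2 model), which is not the primary outcome. Clear inflation of the composite needed strongly unequal drop-out. The plan states one drop-out figure, the same reminders and gift cards for all participants, and no notice of assignment until final tasks are done (Blinding).
- *A full fifth of outcomes is always affected.* The phrase "an improvement in at least one reproductive health issue over the 24 week study", and for contraception "during follow up will be considered an improvement for the primary composite outcome", may let a week-12 response count, and daily texts may supply hot flash data. These reduce the distortion without removing it.

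**Conclusion.** The point holds in this form. The stated rule misclassifies dropouts on the three score components and is undefined for contraception, and up to a fifth of primary outcomes depend on it. The defect in the rule follows from the text and needs no simulation. The sizes are illustrative: OR 3.1 to 3.2 against 3.25 at week 24 in the base case with equal component rates, and about 30% too high when one score drives response. They rest on assumed score distributions, issue mix and completely random drop-out, so no general range or direction can be given. Type I error was not examined for the case where one score drives response. This should be fixed before analysis; it does not invalidate the trial.

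**What to change.** Replace the BLUP sentence with wording to this effect: missing follow-up hot flash scores, vaginal scores and both RCAC subscale scores will be multiply imputed (at least 20 sets), with residual draws, by regression on arm, enrollment and 12-week values and indicators of the issues present at enrollment. Missing contraceptive use, in women at risk of unintended pregnancy, will be imputed by a penalised logistic model on arm and 12-week use. The composite will be derived in each set under one stated visit rule, analysed by the planned logistic model and pooled with Rubin's rules.

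The SAP should state the penalty and how bounded scores are handled. Arm belongs in the contraception model as a covariate because separate models would be too sparse: under the step 3 assumptions, 78 × 0.533 × 0.8 ≈ 33 observed control women and 33 × 0.129 ≈ 4 events.

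The cost is SAP wording, modest programming and a slightly larger standard error of the log odds ratio: 0.385 against 0.369 at week 24 and 0.378 against 0.364 at either visit, about 4%. A simplified version (one fertility score, no issue indicators) recovered about 25% vs 52% and was slightly conservative, with type I error about 3%; the exact wording above was not simulated.

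Separately, the fertility cut-off is ≤3 in YBCS outcome measures and <3 in Statistical Analysis. These must be reconciled before any imputed score is classified.
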